4.2.1.1 Sensitivity Analysis Using Log-rank Test

The primary efficacy analysis will be repeated using a stratified log-rank test at $\alpha = 0.05$ using the stratification at randomization.

4.2.1.2 Sensitivity Analysis for Major Protocol Deviations

The primary efficacy analysis will be repeated for the PP population to assess the impact of subjects with major protocol deviations.

4.2.1.3 Sensitivity Analyses for Missing Data

Our assumptions for missing data and subject discontinuation rates are based on observations from the approximately 2,800 subjects enrolled in studies RM08-3004 and RM08-3005. These studies enrolled a similar population to the one planned for this study, had a similar study design, and used the same diary requirements and strategies to minimize missing diary data.

The majority of missing diary entries in RM08-3004 and RM08-3005 occurred after patient-reported return to usual health, which is consistent with findings in the validation study of FLU-PRO (Powers et al. 2018). Therefore, we expect that most missing data will not be informative regarding symptom course. Subjects missing a single diary entry after the time of Sustained Response had similar responses at the diary entries immediately before and after the missing entry.

A sensitivity analysis will be performed assuming symptom worsening during all periods of potentially meaningful missing data.

Situation	Rule
Subject discontinued study or was lost to follow up prior to achieving Sustained Response	Censored at Day 21 (i.e., hour 504)
Subject discontinued study or was lost to follow up after achieving Sustained Response	Censored at Day 21 (i.e., hour 504)
Subject missed at least two consecutive diary entries after achieving Sustained Response	Assign the Time of Sustained Response to the next non-missing diary after the two consecutive missed diary entries

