### METHODOLOGY

Study Design:	Multicenter, randomized, double-blind trial
----------------------	---------------------------------------------

Treatments:	Subjects will be randomized 1:1 to one of the following groups:  Group 1 (NTZ): Two NTZ 300 mg tablets b.i.d. for 5 days administered orally with food.  Group 2 (Placebo): Two placebo tablets b.i.d. for 5 days administered orally with food.
Study Duration:	Subjects will receive 2 tablets b.i.d. for 5 days (10 doses). The follow up period will extend through the end of study visit at study Day 28.

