## ASSESSMENTS

### Efficacy:

- Subjects will complete a diary recording oral temperature twice daily and the FLU-PRO© patient reported outcomes instrument once daily in the evening for 21 days for efficacy evaluation.
- Subjects will be contacted daily by site staff on study days 2-7 to screen for progression to severe illness or other complications.

**Virology:** Nasopharyngeal swab samples will be collected on each of study Days 1, 4, and 10 for analysis of virology endpoints.

**Safety:** The safety of study drug administration will be monitored by assessment of adverse events from baseline through the Day 28 study exit, clinical laboratory testing at baseline and on Day 10, physical examinations and vital signs assessments at screening, Day 10 and Day 22 and telephone monitoring/at home visits during Day 2 through Day 7 and Day 28.

**Pharmacokinetics:** On the morning of Day 4 prior to dosing, trough plasma samples will be collected.

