### **8.1.9. Day 28 Subject Contact**

Site staff will contact each subject by telephone on study Day 28 to determine if the subject has experienced any new adverse events, developed severe COVID-19 illness, or required hospitalization for any reason.

If warranted, the Day 28 subject contact may also occur in-person at the clinic or another location as agreed upon by the site and subject.

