1.2 Study Procedures

Screening

Subjects will be screened on Study Day 1. After giving informed consent, the subject will be assigned a subject number and complete the following procedures:

1. Collection of relevant medical history.
2. Physical examination including body measurements and resting vital signs (blood pressure, pulse rate, respiratory rate, oxygen saturation, and oral temperature).
3. Collection of demographic information and smoking history.
4. Completion of the FLU-PRO questionnaire to confirm presence of symptoms required for eligibility.
5. Evaluation according to eligibility (inclusion and exclusion) criteria.

The information collected during the screening period must be current through the time of randomization.

Baseline

At Baseline (Study Day 1, the same day as the screening evaluation) the subject will be randomized and complete the following procedures:

1. Collection of a nasopharyngeal swab sample for virology testing.
2. Collection of blood sample for laboratory safety tests and anti-SARS-CoV-2 antibodies.
3. Collection of a urine sample for routine urinalysis (appearance, glucose, protein and blood).
4. Review and recording of any concomitant medications.
5. Randomization and dispensing of study medication. Subjects will be considered enrolled in the study upon the randomized assignment to a treatment group.
6. Administration of the first dose of study medication with food (< 1 hour after food intake) and a B complex vitamin (Super B-Complex™, Igennus Healthcare Nutrition, Cambridge, UK) under observation of Investigator or a member of Investigator's staff, and entry in the medication administration record.
7. Review/record adverse events.
8. The subject will be instructed regarding the administration of study medication, completion of the electronic subject diary, use of birth control, follow-up visits at Study Days 4, 10, and 22, and on seeking emergency medical care or contacting the study physician or nurse under specific conditions, as listed in the protocol.

Treatment Period: Study Days 2 through 7 (Daily)

Site staff will contact each subject by telephone on study Days 2-7 to verify whether the subject has:

1. Completed all expected doses of study medications.
2. Completed all expected electronic diaries.
3. Worsening symptoms or adverse events warranting an unscheduled visit.
4. Presence of shortness of breath at rest.

Follow-up Visits

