4.0 Analysis of Efficacy

4.1 Efficacy Variables

4.1.1 Primary Efficacy Variable

The primary efficacy variable is the Time to Sustained Response. This is defined as the time in days from the first dose of study medication to the time of the first diary entry meeting all the criteria for a sustained response (i.e., Time of Sustained Response).

Sustained response to treatment is defined as a decrease in the total FLU-PRO score from the previous, subject assessment that symptoms are at least “somewhat better than yesterday”, no oral temperature ≥ 100.4 F in the preceding 24 hours, and no future increase in any of the FLU-PRO domains except within the following levels:

FLU-PRO Domain	Background Level
Body/Systemic	0.56
Throat	0.67
Eyes	0.67
Gastrointestinal	2.00
Head	2.00
Nose	Larger of score at time of response or 0.75
Chest	Score at time of response
Cough	Larger of score at time of response or 1.75

Subjects must have at least one diary following the time of sustained response in which there is no relapse, meaning that a subject cannot achieve sustained response at the last diary entry.

Situation	Censoring rule
Has Time of Sustained Response	Not censored.
Hospitalized due to COVID-19	Censored at Day 21 (i.e., hour 504).
Died (any cause)	Censored at Day 21 (i.e., hour 504).
No Time of Sustained Response	Censored at time of last diary entry without sustained response.

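### Read literally, the missing-data sensitivity rule in SAP 4.2.1.3 could censor at hour 504 a responder whose 21-day diary is complete but who leaves the study only after the diary has ended

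*SAP*

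**What the plan says.** - **The rule.** The table in SAP 4.2.1.3 has three rows. The first covers subjects who leave before responding and the second those who leave afterwards: "Subject discontinued study or was lost to follow up after achieving Sustained Response". Both are censored at Day 21, hour 504. The third row concerns responders who miss two or more diaries in succession, and moves their response time to the next diary received.
- **The stated scope.** The sentence above the table describes the analysis as "assuming symptom worsening during all periods of potentially meaningful missing data".
- **The diary.** The Protocol synopsis (Assessments) has subjects complete FLU-PRO "once daily in the evening for 21 days for efficacy evaluation".
- **The study.** The Protocol synopsis (Methodology) goes further: "The follow up period will extend through the end of study visit at study Day 28". Protocol 8.1.9 adds: "Site staff will contact each subject by telephone on study Day 28". That contact asks about adverse events, severe illness and hospitalization. SAP 1.2 refers only to "follow-up visits at Study Days 4, 10, and 22" and does not list the Day 28 contact.
- **The primary analysis.** In the censoring table of SAP 4.1.1, a subject in the row "Has Time of Sustained Response" is an event. Confirmation needs one later diary without relapse; it needs no visit or call.

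**The concern.** The second row is triggered by study status, not by the state of the diary, and it has no end date. Status is also counted beyond the diary elsewhere: SAP 6.1 measures days in study to completion or discontinuation. A program that joins a disposition flag to the response variable would therefore pick up subjects who left after Day 21.

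Such a subject may have supplied every FLU-PRO score the endpoint can use. Neither the Day 22 visit nor the Day 28 contact is listed as collecting FLU-PRO from anyone, so a subject who stays to Day 28 adds no endpoint data. Recoding only those who leave would treat identical diary evidence in two different ways.

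This is the plan's only check on missing diaries. The other two sensitivity analyses change the test (log-rank) or the population (per protocol). If the check mixes real diary loss with later loss of contact, the primary result could be called fragile, or robust, for a reason unrelated to missing primary data.

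**Working it through.** **Plan figures reproduced.** Hour 504 = 21 × 24. For the sample size, 312 / (1 − 0.10) = 347 and 312 × 1.10 = 344 (both rounded up), consistent with the planned 350. The 312 itself cannot be reproduced, because the Kaplan-Meier inputs in Protocol Figure 2 are not shown.

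**One subject traced through the rules.** Response at hour 100, all 21 diaries complete without relapse, formal withdrawal on Day 23.

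- Primary analysis (SAP 4.1.1): event at hour 100.
- Second row read literally: censored at hour 504. With a first dose between 09:00 and 17:00 and a 20:00 diary (assumed times), the last diary falls at hour 20 × 24 + 20 − 9 = 491 down to 20 × 24 + 20 − 17 = 483. Censoring therefore comes after every possible response. A rank test treats this as never having responded.
- Second row read within its lead-in sentence: no diary is missing, so the row does not apply and the event stays at hour 100.

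The two readings give different data for the same subject, and the SAP does not say which to program.

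**Illustrative size.** Inputs from the documents: 156 per group (Protocol 9.1, SAP 1.3) and two-sided 0.05 (Protocol 9.1). Assumptions: exponential response times in whole days; a placebo median of 8.5 or 9 days (Protocol 2.2.4 gives 201.8 h, or 201.8 / 24 = 8.4 days, in a coronavirus subgroup); a response-rate ratio of 1.55, chosen because it gives about 90% power; last possible response on Day 20; an unstratified Gehan-Wilcoxon test. The loss rates are also assumed, because the documents give none.

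Expected number recoded, with a 9-day median:

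- Placebo responders: 1 − 2^(−20/9) = 0.786
- NTZ responders: 1 − 2^(−1.55 × 20/9) = 0.908
- Total responders: 156 × (0.786 + 0.908) = 264
- At 2%, 3%, 5% and 10% loss: about 5, 8, 13 and 26 subjects

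Simulated rejection rates, with 1,500 to 4,000 runs per setting (Monte Carlo error about 0.01). Ranges span the runs and the two medians.

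| Responders lost only after the diary (NTZ / placebo) | Sensitivity test rejects |
|---|---|
| none | about 0.90 |
| 2% / 2% | 0.89 |
| 3% / 3% | 0.88 to 0.89 |
| 5% / 5% | 0.83 to 0.87 |
| 10% / 10% | 0.80 to 0.82 |
| 8% / 3% | 0.63 to 0.66 |
| 3% / 8% | 0.96 |
| no true effect, equal loss | 0.05 |
| no true effect, 2% / 1% | about 0.05 |
| no true effect, 8% / 3% | 0.09 to 0.10 |

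With 350 subjects and equal loss of 1%, 2% or 5%, the sensitivity test keeps about 93%, 91% or 90% power.

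**First row.** A non-responder with a full diary is censored at the last diary in the primary analysis and at hour 504 here. SAP 4.1.1 does not allow a response at the last diary, so no event lies between the two times and the rank test is unchanged.

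**The case against.** The best defence is the lead-in sentence. It limits the analysis to meaningful missing data, the section is titled accordingly, and a complete diary contains no such period. On that reading the table never reaches the subject traced above. This stands in part: it shows the likely intent, and it means that the loss of these responses is not a settled effect of the plan. It does not remove the problem. The third row names diary entries and the second does not, so the second row can fairly be coded on disposition alone.

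Three stronger readings are tempting and are not supported:

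- **That missing the Day 28 call alone triggers the row.** No section says that one missed contact makes a subject lost to follow-up, and the SAP's own schedule ends at Day 22. Formal withdrawal after Day 21 is the firmer example.
- **That the trial's error rate is inflated.** The 9% to 10% figure belongs to a supportive analysis with no success rule attached, under an assumed imbalance. The key secondary test depends on the primary result only (SAP 4.2.2.1).
- **That large distortion is to be expected.** The whole allowance for early discontinuation and missing data is about 10%, so 10% loss falling entirely after Day 21 is an extreme case. A five-point imbalance in the week after the diary, in a double-blind trial of a 5-day course, has no support in the documents.

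It could also be said that Protocol 4.2.7 requires response to last for the remainder of the study. But no FLU-PRO is scheduled after Day 21 for any subject, so later loss of contact removes no endpoint data.

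**Conclusion.** The point holds as a conflict between the second row of the table and the sentence that introduces it. If the row is programmed as written, an observed and confirmed response can be recoded as the worst outcome although no primary data are missing.

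The reach is limited to this one sensitivity analysis. The primary analysis keeps the response as an event, and no alpha, power or sample size figure in the documents is wrong because of it. Equal post-diary loss costs the check some power and leaves its error rate at 5%; only unequal loss biases it. Whether the effect is negligible or noticeable depends on loss rates that the documents do not give, and the simulated sizes also rest on the assumed curves and an unstratified test. The clause is worth adding because it is cheap and no other planned analysis addresses missing diaries.

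**What to change.** In SAP 4.2.1.3, before unblinding:

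1. Reword the second row so that it applies only to responders who left the study or were lost **and** whose diary data stop before the end of the 21-day diary period. A single missed final entry should not count as stopping. This matches the section's view that isolated missed entries are benign, and avoids resetting a responder who lacks only the Day 21 entry.
2. Add that withdrawal or loss of contact after the diary period does not by itself change the time used.
3. Add that the third row still applies to gaps of two or more consecutive diaries, so that the sentence in item 2 is not read as overriding it.
4. Leave the first row unchanged; a diary condition there would gain essentially nothing.

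The cost is a short SAP edit and one date condition in the derivation program, using diary dates that the primary censoring already requires. No new data are needed.

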4.2.2 Key Secondary and Exploratory Efficacy Analysis

All key secondary and exploratory efficacy analyses will be performed for the ITT population.

4.2.2.1 Key Secondary Efficacy Analysis: Proportion of Subjects Progressing to Severe COVID-19 Illness

The cross-tabulation (i.e., two-way table) of Progression to Severe COVID-19 illness versus treatment group will be provided, with conditional rates of progression for each treatment group.

If the primary efficacy analysis is statistically significant at $\alpha=0.05$, the key secondary efficacy variable (Progression to Severe COVID-19 Illness) will be analyzed. The proportion of subjects in the NTZ and placebo groups experiencing progression to severe

COVID-19 illness will be analyzed using a CMH test stratified by randomization stratum with appropriate continuity correction at an unadjusted $\alpha=0.05$. The hypotheses tested are

$$H_0: p_{NTZ} = p_{Ctl}$$
$$H_1: p_{NTZ} \neq p_{Ctl},$$

where p_{NTZ} and p_{Ctl} respectively represent the rate at which NTZ subjects and placebo subjects progress to severe COVID-19 illness. The overall odds ratio and a 95% confidence interval for the odds ratio will be provided.

4.2.2.2 Exploratory Analysis: Proportion of subjects Positive for SARS-CoV-2 by Aptima® SARS-CoV-2 Assay at Days 4 and 10

Nasopharyngeal swabs for virology testing are scheduled to be taken on the Day 4 and Day 10 visits. The rates at which subject nasopharyngeal swabs test positive for SARS-CoV-2 in the NTZ and placebo groups will be analyzed using a CMH test stratified by the randomization stratum with the appropriate continuity correction at an unadjusted α of 0.05. The hypotheses tested are

$$H_0: p_{NTZ} = p_{Ctl}$$
$$H_1: p_{NTZ} \neq p_{Ctl},$$

where p_{NTZ} and p_{Ctl} respectively represent the rate at which NTZ subjects and placebo subjects test positive by the Aptima® SARS-CoV-2 assay. The overall odds ratio and a 95% confidence interval for the odds ratio will be provided. The cross-tabulation of SARS-CoV-2 status versus treatment group will be provided, with conditional rates for each treatment group. Day 4 and Day 10 data will be analyzed separately.

4.2.2.3 Exploratory Analysis: Changes from Baseline in Quantitative SARS-CoV-2 RNA Measured by RT-PCR

Viral RNA levels will be determined for the Day 4 and Day 10 nasopharyngeal swabs by quantitative RT-PCR. The reported value will be transformed by $\log_{10}(X+1)$, where X is the reported number of RNA copies/ μ L. The transformed values will be summarized with descriptive statistics (number of observations, mean, standard deviation, minimum, maximum, median) by treatment group. A Satterthwaite T-test will be used to test the hypotheses

$$H_0: \mu_{NTZ} = \mu_{Ctl}$$
$$H_1: \mu_{NTZ} \neq \mu_{Ctl},$$

where μ_{NTZ} and μ_{Ctl} respectively represent the mean $\log_{10}(\text{RNA copies}/\mu\text{L})$ concentrations for the NTZ and placebo groups. A 95% confidence interval for the difference in means will be provided.

4.2.2.4 Exploratory Analysis: Proportion of Subjects Hospitalized Due to COVID-19 or Complications Thereof

The cross-tabulation of Hospitalization due to COVID-19 illness or complications thereof versus treatment group will be provided, with conditional rates for each treatment group.

Hospitalization due to COVID-19 or complications thereof will be analyzed using a CMH test stratified by the randomization stratum with the appropriate continuity correction at an unadjusted α of 0.05. The hypotheses tested are

$$\begin{aligned} H_0: p_{NTZ} &= p_{Ctl} \\ H_1: p_{NTZ} &\neq p_{Ctl} \end{aligned}$$

where p_{NTZ} and p_{Ctl} respectively represent the rate at which NTZ subjects and placebo subjects are hospitalized due to COVID-19 illness or its consequences. The overall odds ratio and a 95% confidence interval for the odds ratio will be provided.

4.2.2.5 Exploratory Analysis: Proportion of Subjects with Mortality Due to COVID-19 or Complications Thereof

The cross-tabulation of Mortality due to COVID-19 illness or complications thereof versus treatment group will be provided, with conditional rates for each treatment group.

Mortality due to COVID-19 or complications thereof will be analyzed using a CMH test stratified by the randomization stratum with the appropriate continuity correction at an unadjusted α of 0.05. The hypotheses tested are

$$\begin{aligned} H_0: p_{NTZ} &= p_{Ctl} \\ H_1: p_{NTZ} &\neq p_{Ctl} \end{aligned}$$

where p_{NTZ} and p_{Ctl} respectively represent the rate at which NTZ subjects and placebo subjects die due to COVID-19 illness or its consequences. The overall odds ratio and a 95% confidence interval for the odds ratio will be provided.

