#### 9.4.1. Efficacy Analyses

Efficacy analyses will be based on a population consisting of all subjects randomized who receive at least one dose of study medication and are positive for SARS-CoV-2 by Aptima® SARS-CoV-2 Assay at Baseline. For time-to-event analyses, a test of significance (as described in the following) will be performed with descriptive statistics provided, including the use of Kaplan-Meier figures.

There will be one primary efficacy analysis:

- Time to Sustained Response for the NTZ treatment group will be compared to that of the placebo treatment group using a stratified Gehan-Wilcoxon test ( $\alpha=0.05$ ) where stratification will follow that used for randomization. Subjects without a Sustained Response recorded will be treated as censored as of the last diary without a documented Sustained Response, except for subjects who are hospitalized or die during the study, who will be censored at Day 21 (hour 504).

Sensitivity analyses for the primary efficacy analysis will be described in the Statistical Analysis Plan.

If the primary analysis is significant at the 0.05 level, the key secondary efficacy analysis will be formally evaluated at the 0.05 level as follows:

- Proportions of subjects progressing to Severe COVID-19 Illness will be compared between the treatment groups using a Cochran-Mantel-Haenszel (CMH) test stratified by the randomization strata.

Exploratory analyses will be performed as follows:

- Proportions of subjects positive for SARS-CoV-2 by Aptima® SARS-CoV-2 Assay at study Day 4 and Day 10 will be compared between the treatment groups using a Cochran-Mantel-Haenszel (CMH) test stratified by the randomization strata.
- Mean changes from baseline in quantitative SARS-CoV-2 RNA measured by RT-PCR at Day 4 and Day 10 will be compared using a t-test.
- Proportions of subjects hospitalized due to COVID-19 or complications thereof will be compared across the treatment groups using a CMH test stratified by the randomization strata.
- Proportions of subjects with mortality related to COVID-19 or complications thereof will be compared across the treatment groups using a CMH test stratified by the randomization strata.

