2.2 Analysis Populations

2.2.1 Population Definitions

Subjects will be considered enrolled in the study upon completion of the baseline procedures. The following analysis populations will be used in the study.

- **Intent-to-Treat (ITT) Population** – the ITT population includes all subjects who are enrolled in the study and have received at least one dose of study medication (NTZ or placebo).
- **Intent-to-Treat Infected (ITI) Population** – the ITI population includes all ITT subjects who are positive for SARS-CoV-2 by Aptima® SARS-CoV-2 assay at Baseline.
- **Per Protocol (PP) Population** – the subset of the ITI population with no major protocol deviations that may affect the integrity of the data or evaluation of effectiveness. Exclusion from the PP will be done before database lock.

The ITT population will be used for all safety analyses. The ITI population will be the primary population for all efficacy analyses.

Data listings displaying the subjects excluded from each population will be created. These listings will be relative to all subjects enrolled in the study.

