8.0 List of Analysis Tables, Figures and Listings

Table No.	Table Title
14.1.1.1	Subject Disposition Summary by Treatment and Overall (ITT Population)
14.1.1.2	Subject Disposition Summary by Treatment and Overall (ITI Population)
14.1.2.1	Summary of Protocol Deviations (ITT Population)
14.1.2.2	Summary of Protocol Deviations (ITI Population)
14.1.3.1	Summary of Baseline Demographic Characteristics (ITT Population)
14.1.3.2	Summary of Baseline Demographic Characteristics (ITI Population)
14.1.4.1	Summary of Prior Medication (ITT Population)
14.1.4.2	Summary of Prior Medication (ITI Population)
14.1.5.1	Summary of Concomitant Medication (ITT Population)
14.1.5.2	Summary of Concomitant Medication (ITI Population)
14.1.6.1	Summary of Medical History (ITT Population)
14.1.6.2	Summary of Medical History (ITI Population)
14.1.7.1	Summary of Concomitant Diseases (ITT Population)
14.1.7.2	Summary of Concomitant Diseases (ITI Population)
14.1.8.1	Summary of Treatment Compliance (ITT Population)
14.1.8.2	Summary of Treatment Compliance (ITI Population)
14.2.1.1.1	Analysis of Time to Sustained Response (ITI Population)
14.2.1.2.1	Analysis of Time to Sustained Response by Subgroups (ITI Population)
14.2.2.1.1	Sensitivity Analysis of Time to Sustained Response Using a Log-rank Test (ITI Population)
14.2.2.2.1	Sensitivity Analysis of Time to Sustained Response for the Per Protocol Population (PP Population)
14.2.2.3.1	Sensitivity Analysis of Time to Sustained Response to Assess the Impact of Missing Data (ITI Population)
14.2.3	Cochran-Mantel-Haenszel Test Results: Proportion of Subjects Progressing to Severe COVID-19 Illness (ITI Population)
14.2.4.1	Cochran-Mantel-Haenszel Test Results: Proportion of Subjects Positive for SARS-CoV-2 by Aptima SARS-CoV-2 Assay at Day 4 (ITI Population)
14.2.4.2	Cochran-Mantel-Haenszel Test Results: Proportion of Subjects Positive for SARS-CoV-2 by Aptima SARS-CoV-2 Assay at Day 10 (ITI Population)

Table No.	Table Title
14.2.5.1	Summary of Quantitative SARS-CoV-2 RNA Measured by RT-PCR by Treatment (ITT Population)
14.2.5.2	Satterthwaite T-test Results: Change from Baseline in Quantitative SARS-CoV-2 RNA Measured by RT-PCR at Day 4 and Day 10 (ITT Population)
14.2.6	Cochran-Mantel-Haenszel Test Results: Proportion of Subjects Hospitalized Due to COVID-19 or Complications Thereof (ITT Population)
14.2.7	Cochran-Mantel-Haenszel Test Results: Proportion of Subjects with Death Due to COVID-19 or Complications Thereof (ITT Population)

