14.2.8	Summary of SARS-CoV-2 IgG and IgM Antibodies Raw and Change from Baseline Values (ITT Population)
14.2.9	Analysis of Plasma Tizoxanide and Tizoxanide Glucuronide Concentrations (ITT Population)
14.3.1.1	Summary of All Treatment Emergent Adverse Events (ITT Population)
14.3.1.2	Treatment Emergent Adverse Events by System Organ Class, Preferred Term, and Treatment (ITT Population)
14.3.1.3	Treatment Emergent Adverse Events by System Organ Class, Preferred Term, Treatment, and Severity (ITT Population)
14.3.1.4	Treatment Emergent Adverse Events by System Organ Class, Preferred Term, Treatment, and Relationship to Treatment (ITT Population)
14.3.1.5	Treatment Emergent Serious Adverse Events by System Organ Class, Preferred Term, and Treatment (ITT Population)
14.3.2.1	Clinical Laboratory Summary Statistics: Hematology by Treatment (ITT Population)
14.3.2.2	Clinical Laboratory Shift Tables: Hematology by Treatment (ITT Population)
14.3.3.1	Clinical Laboratory Summary Statistics: Clinical Chemistry by Treatment (ITT Population)
14.3.3.2	Clinical Laboratory Shift Tables: Clinical Chemistry by Treatment (ITT Population)
14.3.4.1	Clinical Laboratory Summary Statistics: Urinalysis by Treatment (ITT Population)
14.3.4.2	Clinical Laboratory Shift Tables: Urinalysis by Treatment (ITT Population)
14.3.5	Vital Signs Summary Statistics for Raw and Change from Baseline Values by Treatment (ITT Population)
14.3.6	Physical Examination Shift Tables by Treatment (ITT Population)

Listing No.	Data Listing Title
16.2.1	Discontinued Subjects (ITT Population)
16.2.2	Protocol Deviations Listing (ITT Population)
16.2.3	Subjects Excluded from the ITI and PP Populations (ITT Population)
16.2.4.1	Subject Demographics Listing (ITT Population)
16.2.4.2	Medical History Listing (ITT Population)
16.2.4.3	Prior and Concomitant Medications Listing (ITT Population)
16.2.5.1	Treatment Exposure Listing (ITT Population)
16.2.5.2	Plasma Tizoxanide and Tizoxanide Glucuronide Listing (ITT Population)
16.2.6.1	Subject Primary Efficacy and Sensitivity Analysis Variables Listing: Time to Sustained Response (ITI Population)
16.2.6.2	Subject Secondary Efficacy Variables Listing: Progression to Severe COVID-19 Illness (ITI Population)
16.2.6.3	Subject Exploratory Efficacy Variables Listing: Hospitalization Status, Mortality (ITI Population)
16.2.7.1	Adverse Events Listing (ITT Population)
16.2.7.2	Serious Adverse Events Listing (ITT Population)
16.2.7.3	Subject Deaths Listing (ITT Population)

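### SAP 4.2.2 runs the gated key secondary test in all dosed subjects, while the protocol and the SAP's other entries for that test use SARS-CoV-2-positive subjects only

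*SAP*

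**What the plan says.** Progression to Severe COVID-19 Illness is the key secondary endpoint. It is tested at 0.05 only if the primary analysis is significant (Protocol 9.4.1; SAP 4.2.2.1). Its analysis population is stated in five places:

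| Place | Population for the key secondary |
|---|---|
| SAP 4.2.2 | ITT: "All key secondary and exploratory efficacy analyses will be performed for the ITT population" |
| Protocol 9.4.1 | Randomized and dosed subjects who "are positive for SARS-CoV-2 by Aptima® SARS-CoV-2 Assay at Baseline" |
| SAP 2.2.1 | ITI: "The ITI population will be the primary population for all efficacy analyses" |
| SAP 8.0, Table 14.2.3 (the CMH result) | ITI |
| SAP 8.0, Listing 16.2.6.2 | ITI |

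SAP 2.2.1 defines the wider set without reference to infection: "the ITT population includes all subjects who are enrolled in the study and have received at least one dose of study medication". ITI is its Baseline-positive subset. The protocol does not use the term ITI, but its definition is the same set.

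The exploratory outputs in SAP 8.0 are split. The Aptima tables (14.2.4.1, 14.2.4.2) and the hospitalisation and mortality efficacy listing (16.2.6.3) are ITI. The RNA tables (14.2.5.1, 14.2.5.2) and the hospitalisation and death tables (14.2.6, 14.2.7) are ITT.

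**The concern.** Taken literally, SAP 4.2.2 puts SARS-CoV-2-negative subjects into the only alpha-controlled secondary test, against the protocol. The severe-illness definition (Protocol 9.3; SAP 4.1.2) is breathlessness at rest plus an oxygenation threshold, with no virological confirmation. A Baseline-negative subject who meets both criteria would be counted as progressing to severe COVID-19. The quantity estimated also changes, from an effect in infected patients to an effect diluted by people without the disease.

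Either population gives a valid test if it is fixed in advance. The risk is that the choice between two written populations is made after results are known.

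**Working it through.** **1. Can the texts be reconciled?** SAP 2.2.1 calls ITI the primary population, which leaves room for a supplementary ITT analysis. That does not resolve the conflict: SAP 4.2.2 names ITT alone, and Table 14.2.3, which reports the same test, is ITI. ITT could be a slip for ITTI, a spelling the SAP uses for the infected set in 3.0 and 6.1, among others. But four exploratory tables do carry the ITT label, so the intent cannot be read off with certainty.

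**2. The plan's own numbers.** 312/(1 − 0.10) = 347, which agrees with the stated minimum of 350 infected. 400/0.50 = 800 matches the stated upper enrolment. 350/0.75 = 467, where the plan says 450; that figure would need 350/450 = 77.8% positive. I use 467.

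**3. Size of the two sets**, taking 350 infected and assuming all enrolled subjects are dosed:
- 75% positive: ITT 467, negatives 467 − 350 = 117 (25%).
- 50% positive: ITT 700, negatives 700 − 350 = 350 (50%).

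**4. Dilution.** Let f be the positive fraction, p the event rate in infected subjects and u the rate in negatives. The ITT rate is f·p + (1 − f)·u. If u is equal in both arms, the ITT risk difference is f times the ITI difference, so 50–75% of it. Neither document gives a severe-illness rate; the rates below are assumptions. For infected 5% (placebo) v 1% (NTZ) and u = 1%:
- f = 0.75: 4% v 1%, a difference of 3 points instead of 4.
- f = 0.50: 3% v 1%, a difference of 2 points.

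**5. Uncorrected power.** Two-sided 0.05, n per arm = 175/f, p̄ the mean of the two rates:

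Φ{ [ |p₁ − p₂|√n − 1.96√(2p̄(1 − p̄)) ] / √(p₁(1 − p₁) + p₂(1 − p₂)) }

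At infected 5% v 1%:
- ITI: 0.593.
- ITT, u = 0: 0.589 (f = 0.75), 0.586 (f = 0.50).
- ITT, u = 1%: 0.546 (f = 0.75), 0.472 (f = 0.50).

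**6. The SAP's test.** Continuity-corrected stratified CMH, 300,000 simulated trials, eight equal strata (an assumption), 22 infected per arm per stratum (176 per arm; ITT 232 or 352 per arm). Paired entries are for 75% and 50% positive.

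| Infected rates | Power, ITI | Power, ITT, u = 0 | Power, ITT, u = 1% | Sets disagree, u = 0 | Sets disagree, u = 1% |
|---|---|---|---|---|---|
| 3% v 1% | 0.135 | 0.136, 0.135 | 0.127, 0.111 | 0%, 0% | 6.3%, 10.7% |
| 5% v 1% | 0.488 | 0.488, 0.487 | 0.443, 0.369 | 0%, 0.1% | 11.4%, 21.1% |
| 8% v 2% | 0.677 | 0.675, 0.663 | 0.644, 0.571 | 0.3%, 1.4% | 8.0%, 16.7% |

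At u = 0.2% the sets disagree in 1.8–8.2% of trials. Disagreement runs both ways: of the 21.1%, 16.5% are significant in ITI only and 4.6% in ITT only.

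**7. False positives.** With no effect (infected 3% or 5% in both arms, u from 0 to 1%), claiming success if either set is significant gives 0.021–0.037 with the correction, against 0.020–0.028 for one set alone. Without the correction, the either-set rate is 0.046–0.069.

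**The case against.** The best counter-argument is that this is a labelling slip. Every other statement about the key secondary says ITI, ITT is one letter from ITTI, and the protocol lets a reader recover the rule. That is plausible, but the four ITT exploratory titles agree with 4.2.2, so it is not proven.

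Second, the numerical harm rests on rates the documents do not give. If negatives have no events, power is essentially unchanged and the sets almost never disagree. The 21.1% figure needs the lowest planned positivity and a 1% event rate in negatives, equal to the rate assumed for treated infected subjects. This stands: the simulations show what could happen, not what is expected.

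Third, the SAP specifies a continuity correction, and with it the either-set rate stays below 0.05. The simulation also ignores the gate, which limits the error further when the primary null is true. This stands too.

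Fourth, Protocol 4.1 expects many Enterovirus/Rhinovirus-positive subjects and sends their data to study RM08-3009. Applying that rule would reduce the negatives by an amount the documents do not give. But the ITT definition in the SAP does not exclude those subjects, so 117–350 is what the SAP text yields.

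Fifth, the exploratory mismatch is mostly housekeeping. Protocol 8.2.2.2 schedules Day 4 and Day 10 SARS-CoV-2 testing only for Baseline-positive subjects, and 8.2.2.3 quantifies only positive samples, so relabelling the RNA tables should not alter their test. Hospitalisation and death count only when attributed to COVID-19. None of these tests carries confirmatory alpha. I agree, and treat those titles as secondary.

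**Conclusion.** The concern holds and should be fixed before unblinding. The contradiction is in the text and depends on no calculation: the single gated secondary test is assigned to ITT in SAP 4.2.2 and to Baseline-positive subjects in four other places, including the protocol. Following 4.2.2 would make 25–50% of the analysed subjects uninfected at the planned positivity, and would shrink the risk difference to 50–75% of its value in infected subjects if event rates in negatives are equal between arms.

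The effect on power and on the conclusion runs from negligible (no events in negatives) to material (1% events, 50% positive), and rests on assumed rates and equal strata. No inflation above 0.05 is claimed for the continuity-corrected test.

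**What to change.** Must change: in the first sentence of SAP 4.2.2, replace ITT with ITI, so that it agrees with Protocol 9.4.1, SAP 2.2.1, Table 14.2.3 and Listing 16.2.6.2.

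For alignment: make the same replacement in the titles of Tables 14.2.5.1, 14.2.5.2, 14.2.6 and 14.2.7, and use one name for the infected set throughout (ITI rather than ITTI). All-dosed hospitalisation and death tables may be kept if labelled supportive; the ITT safety listings of serious adverse events and deaths (16.2.7.2, 16.2.7.3) need no change.

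The cost is one sentence, four titles and a consistent abbreviation, with no new data. It should be done before any unblinded output is produced, because SAP 2.4.1 lets the sponsor receive unblinded tables before the late laboratory data arrive.
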